# The Effects of Other Drugs on Palbociclib

Palbociclib is primarily metabolized by CYP3A and sulfotransferase (SULT) enzyme SULT2A1.

The use of strong CYP3A inhibitors (e.g., clarithromycin, indinavir, itraconazole, ketoconazole, lopinavir/ritonavir, nefazodone, nelfinavir, posaconazole, ritonavir, saquinavir, telaprevir, telithromycin, verapamil, and voriconazole) should be avoided as these drugs could increase plasma levels of palbociclib.

The use of strong CYP3A inducers (e.g., phenytoin, rifampin, carbamazepine and St John's Wort) or moderate CYP3A inducers (e.g., bosentan, efavirenz, etravirine, modafinil, and nafcillin) should be avoided as these drugs could decrease plasma levels of palbociclib.

The use of strong inhibitors or inducers of CYP2D6 (Bupropion, dacomitinib, fluoxetine, paroxetine, quinidine) should be avoided

# The Effects of Palbociclib on Other Drugs

In vivo, palbociclib is a time-dependent inhibitor of CYP3A.

Coadministration of midazolam with multiple doses of palbociclib increased the midazolam plasma exposure by 61%, in healthy subjects, compared with administration of midazolam alone. The dose of the sensitive CYP3A substrate with a narrow therapeutic index (e.g., alfentanil, cyclosporine, dihydroergotamine, ergotamine, everolimus, fentanyl, pimozide, quinidine, sirolimus and tacrolimus) may need to be reduced as palbociclib may increase their exposure.

#### **Prohibited Concomitant Medications**

Subjects are prohibited from receiving the following therapies during the Screening and Treatment Phase of this trial:

- Anti-cancer systemic chemotherapy or biological therapy not specified in this protocol
- Other investigational and antineoplastic therapies

Subjects who, in the assessment by the investigator, require the use of any of the aforementioned treatments for clinical management should be removed from the trial.

There are no prohibited therapies during the Post-Treatment Follow-up Phase.

# 5.6. Diet/Activity/Other Considerations

#### Diet

Subjects should maintain a normal diet unless modifications are required to manage an AE such as diarrhea, nausea, or vomiting.

#### Contraception

Palbociclib may have adverse effects on a fetus in utero. Non-pregnant, non-breast-feeding women may be enrolled if they are willing to use 2 methods of birth control or are considered highly unlikely to conceive. Highly unlikely to conceive is defined as 1) surgically sterilized, or 2) postmenopausal (a woman who is ≥45 years of age and has not had menses for greater than 1 year will be considered postmenopausal), or 3) not heterosexually active for the duration of the study.

It is encouraged but not mandatory that premenopausal subjects will also receive treatment with goserelin or equivalent (e.g. Lupron) given as an injectable subcutaneous implant on day 1 of every 28 days cycle or every 3 months.

The following are considered adequate barrier methods of contraception: diaphragm, condom (by the partner), copper intrauterine device, sponge, or spermicide. The use of hormonal contraceptives is discouraged.

Subjects should be informed that taking the study medication may involve unknown risks to the fetus (unborn baby) if pregnancy were to occur during the study. In order to participate in the study they must adhere to the contraception requirements described above for the duration of the study and at least 120 days following the last dose of study drug. If there is any question that a subject will not reliably comply with the requirements for contraception, that subject should not be entered into the study.

# **Use in Pregnancy**

If a subject becomes pregnant while on treatment with palbociclib, the subject will immediately be removed from the study therapy. All pregnancies must be reported to BTCRC AHQ within 1 business day using the Pregnancy Report form (See Documents/Info tab of the EDC).

The study investigator will make every effort to obtain permission to follow the outcome of the pregnancy and report the condition of the fetus or newborn to BTCRC AHQ. The site should make every effort to contact the subject at least monthly and document the subject's status until the pregnancy has been completed or terminated. The outcome of the pregnancy will be reported to BTCRC AHQ as soon as the information is available. If the outcome is a serious adverse event (e.g., death, abortion, congenital anomaly, or other disabling or life-threatening complication to the mother or newborn), it will be reported to BTCRC AHQ within 1 business day.

# **Use in Nursing Women**

It is unknown whether palbociclib is excreted in human milk. Since many drugs are excreted in human milk, and because of the potential for serious adverse reactions in the nursing infant, subjects who are breast-feeding are not eligible for enrollment.

#### 6. DOSE DELAYS

The NCI Common Terminology Criteria for Adverse Events (CTCAE) Version 4 will be used to grade adverse events.

Subjects enrolled in this study will be evaluated clinically and with standard laboratory tests before and at regular intervals during their participation in this study as specified in Section 7.

Subjects will be evaluated for adverse events (all grades), serious adverse events, and adverse events requiring protocol therapy interruption or discontinuation at each study visit for the duration of their participation in the study.

Subjects discontinued from the study drug for any reason will be evaluated within 30 days ( $\pm$  7) of the last dose of study drug.

#### **6.1.** Dose Modifications

#### 6.1.1. Palbociclib Dose Modifications

**Table 1. Dose Modifications for Adverse Reactions** 

Dose Level	Dose		
Recommended starting dose	125 mg/day		
First dose reduction	100 mg/day		
Second dose reduction 75 mg/day *			
*If further dose reduction below 75 mg/day is required, the subject will be			

\*If further dose reduction below 75 mg/day is required, the subject will be discontinued from study treatment.

Palbociclib will be withheld for drug-related >Grade 3 hematologic toxicities, non-hematological toxicity >Grade 3 including laboratory abnormalities and severe or life-threatening AEs as per Table 2 below.

Table 2: Dose modification guidelines for drug-related adverse events.

Toxicity	Grade	Hold Treatment (Y/N)	Timing for restarting treatment	Dose/Schedule for restarting treatment	Discontinue Subject
Hematological	1, 2	No	N/A	N/A	N/A
Toxicity	3* *Except lymphopenia (unless associated with clinical events, e.g, opportunistic infections)	Withhold initiation of next cycle.  Repeated hematologic monitoring one week later	Toxicity resolves to Grade ≤2	No dose adjustment is required	Toxicity does not resolve within 4 weeks of last study drug administration Permanent discontinuation should be considered for any
	Grade 3 ANC (<1000 to 500/mm³) + Fever>38.5° C and/or infection  Grade 3 Plt count (<50000 to 25000/mm³) with clinically	Yes	Toxicity resolves to Grade \leq 2 (ANC > 1000/ mm  , platelets > 50000/mm  )	Resume at next lower dose	severe or life- threatening event
	significant bleeding  4*  *Except lymphopenia (unless associated with clinical events, e.g, opportunistic infections)	Yes	Toxicity resolves to Grade ≤2	Resume at next lower dose	
Non-	1,2	No	N/A	N/A	N/A
hematological toxicity†  Note: Exception to be treated similar to grade 1 toxicity  Grade 2 alopecia Grade 2 fatigue	3,4 (if persisting despite medical treatment)	Yes	Toxicity resolves to:  • Grade ≤1; • Grade ≤2 (if not considered a safety risk for the subject)	Resume at next lower dose	Toxicity does not resolve within 4 weeks of last study drug administration Permanent discontinuation should be considered for any severe or life-threatening event

Footnotes:  $\dagger$ Concurrent elevation of bilirubin > 2x ULN and ALT > 3 x ULN in absence of an evident alternative explanation (such as liver mets) will lead to discontinuation of the study drugs

• Complete blood count will be monitored prior to start of study treatment and at the beginning of each cycle, as well as on Day 15 of the first two cycles, and as clinically indicated.

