# 7. STUDY CALENDAR & EVALUATIONS

[Cycle = 28 days]							T		
	Scree	ening	Cycle 1	Cycle 2	Cycle 3-5	Every 2 cycles	Every 3 cycles	Safety follow up	Long-Term follow up
Study Day	-28 days	-14 days	Day 1 	Day 1 (±3)	Day 1 (±3)	(± 7)	(± 7)	30 days (±7) post last study drug	Every 3 months (±14) for 2 years from registration
REQUIRED ASSESSMENTS									
Informed Consent/ HIPAA auth.	X								
Medical hx including prior therapies; pathology	X								
Physical examination	X		X	X	X	C7+		X	
Vital Signs, weight, height (screen only)	X		X	X	X	C7+		X	
ECOG status	X		X	X	X	C7+		X	
Baseline signs/ symptoms; AE assessment	X		X	X	X	C7+		$X^5$	
Concomitant medications	X		X	X	X	C7+		X	
Survival									$X^6$
LABORATORY TESTS									
Blood Chemistries 		X	X	X	X	C7+			
Platelets, ANC & Hgb 		X	D1, D15	D1, D15	X	C7+			
Pregnancy test for WOCP 		-72h	X	X	X	C7+			
DISEASE ASSESSMENT 						C3-19	C22+		
CT/MRI chest, abdomen/pelvis	X					$X^8$	$X^8$		X
CT or MRI Brain, if clinically indicated	X								
Whole body bone scan	X					$X^{8,9}$	$X^{8,9}$		
Bone x-ray, CT, or MRI 	X					$X^8$	$X^8$		
Skin color photography, if applicable	X					$X^8$	$X^8$		
TREATMENT EXPOSURE									
Palbociclib (Day 1-21)			X	X	$X^{16}$	$C7+^{16}$			
Tamoxifen (Continuous)			х —		—	C7+			
CORRELATIVE STUDIES (SPECIMEN COI	LLECTI	ION)					C8, 11, etc.		
Tumor tissue (unstained slides) 			X					$X^{11}$	
Blood for circulating tumor DNA 			X		C5		$X^{12}$	$X^{12}$	
BANKING SAMPLES (SPECIMEN COLLECTION)									
Whole Blood 			X						
Unstained Slides  (archival, if available)			X						
Serum and Plasma 			X					X	

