- 12: Blood for circulating tumor DNA will be collected cycle 1 day 1, cycle 5 day 1 and day 1 of every subsequent 3rd cycle (e.g. cycle 8, 11, etc.), and at time of progression.
- 13: Submission of whole blood for banking is to be collected at Pre-Treatment Cycle 1 Day 1. See CLM for collection, processing, labeling and shipping instructions.
- 14: Submission of unstained slides for banking from an archived FFPE tumor block (if available). See CLM for collection, labeling, and shipping instructions.
- 15: Submission of serum and plasma for banking are to be collected at Pre-Treatment Cycle 1 Day 1 and at the 30 Day Safety Follow up visit. See CLM for collection, labeling, processing, and shipping instructions.
- 16: After cycle 5, subjects will be assessed every 2 cycles (cycle 7, 9, 11, etc.). Two cycles of palbociclib may be dispensed from cycle 5 onward.

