# 7.2.5. Day 1 of Cycle 3-5 (±3 days)

- Physical exam, weight
- Vital signs
- ECOG performance status
- Blood chemistries (sodium, potassium, serum creatinine calcium, albumin, ALT, AST, bilirubin, alkaline phosphatase)
- Platelets, ANC and hemoglobin
- Pregnancy test for women of childbearing potential (WOCP), if clinically indicated. If
  the urine test is positive or cannot be confirmed as negative, a serum pregnancy test
  will be required.
- Assess adverse events
- Concomitant medications
- Dispense Palbociclib (dispense 2 cycles at cycle 5)
- Prescribe Tamoxifen (commercial supply)
- Correlative blood sample: cycle 5 day 1

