## 7.3. Every two cycles ( $\pm 7$ days)

- Disease assessment will be performed every 2 cycles starting at cycle 3 (cycle 3, 5, 7, etc.) for the first 19 cycles (18 months):
  - o CT/MRI chest, abdomen, pelvis (±7 days).
  - o Whole body bone scan if positive for mets at screening or if clinically indicated.

- o If bone lesion detected from whole body bone scan, repeat bone scan, bone X-ray, CT, or MRI of the largest skeletal lesion identified.
- o If skin lesion detected by physical exam at screening, skin color photography.
- Subjects will be assessed every 2 cycles starting after cycle 5 (cycle 7, 9, 11, etc.):
  - o Physical exam, weight
  - o Vital signs
  - o ECOG performance status
  - o Blood chemistries (sodium, potassium, serum creatinine calcium, albumin, ALT, AST, bilirubin, alkaline phosphatase)
  - o Platelets, ANC and hemoglobin
  - Pregnancy test for women of childbearing potential (WOCP), if clinically indicated. If the urine test is positive or cannot be confirmed as negative, a serum pregnancy test will be required.
  - o Assess adverse events
  - Concomitant medications
  - o Dispense 2 cycles of Palbociclib
  - o Prescribe Tamoxifen (commercial supply)

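### Section 6.1.1 requires a blood count at the start of every cycle, but Section 7 schedules none at Cycles 6, 8, 10 and later even-numbered cycles, where Table 2's Grade 3 hold may have to be applied

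*Combined protocol and SAP*

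**What the plan says.** Three parts of the protocol bear on the timing of blood counts.

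- **Section 6.1.1** (the bullet after Table 2): "Complete blood count will be monitored prior to start of study treatment and at the beginning of each cycle". The rest of that sentence adds Day 15 of the first two cycles and discretionary counts when there is a clinical reason. It does not limit the cycle-start requirement to early cycles.
- **Section 6** (opening text) says that subjects are evaluated "with standard laboratory tests before and at regular intervals during their participation in this study as specified in Section 7".
- **Section 7.** The calendar row "Platelets, ANC & Hgb" has entries at screening, Days 1 and 15 of Cycles 1 and 2, and Day 1 of Cycles 3 to 5. It then has C7+ in the two-cycle column. Footnote 16 says: "After cycle 5, subjects will be assessed every 2 cycles (cycle 7, 9, 11, etc.)". Section 7.3 says the same in prose: "Subjects will be assessed every 2 cycles starting after cycle 5 (cycle 7, 9, 11, etc.)", and includes platelets, ANC and haemoglobin in the list for those visits.

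Dispensing follows the two-cycle visits. Footnote 16 says "Two cycles of palbociclib may be dispensed from cycle 5 onward", and Section 7.2.5 says "Dispense Palbociclib (dispense 2 cycles at cycle 5)".

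For Grade 3 haematological toxicity, Table 2 gives the instruction "Withhold initiation of next cycle", with repeat monitoring one week later.

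**The concern.** The two schedules agree up to Cycle 5 and then part. Table 2 says what to do with a Grade 3 count but does not schedule the count. It depends on the 6.1.1 sentence or on Section 7, and these give different answers for every even-numbered cycle from Cycle 6. At those starts the subject already has the drug at home, and Section 7 lists neither a visit nor a count before the first capsule is taken.

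The hold is not a rule for rare events. Section 10.1 (Neutropenia) reports Grade 3 or worse neutrophil decreases in 66% of patients on palbociclib with letrozole and in 66% with fulvestrant. Those are different partner drugs, and the figures are per patient at any time, so they show only that the rule will be used.

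There is also a compliance question. Section 13.1 has monitors check that key aspects of the protocol are followed, but the text does not tell a monitor whether a missing Cycle 8 count is a deviation.

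**Working it through.** The plan states no figure to reproduce. The check sets the texts side by side and then counts the affected cycle starts.

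**Which cycle starts have a required count**

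| Cycle start | Section 6.1.1 | Section 7 (calendar, footnote 16, 7.2, 7.3) |
|---|---|---|
| 1 to 5 | yes | yes |
| 6, 8, 10, ... | yes | no |
| 7, 9, 11, ... | yes | yes |

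Footnote 3, which belongs to the haematology row, adds only the Day 15 counts in Cycles 1 and 2. Footnote 16 is attached to the palbociclib row, but its wording covers assessments in general, and the haematology row and 7.3 give the same pattern directly. No text in Section 7 puts a count at an even-numbered cycle after Cycle 5.

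**How many starts are affected**

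Inputs: 28-day cycles (Section 7); 15 and 25 months, the null and alternative median PFS in Section 12.3, used here only as illustrative treatment durations; 1 month = 30.44 days (assumption). Cycle k starts on day (k − 1) × 28 if there are no delays.

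- 15 months = 15 × 30.44 = 456.6 days. The last cycle started is Cycle 17, on day 16 × 28 = 448. Cycles 6 to 17 give 12 starts. The even-numbered ones are 6, 8, 10, 12, 14 and 16, so **6** have no scheduled count under Section 7.
- 25 months = 25 × 30.44 = 761 days. The last cycle started is Cycle 28, on day 27 × 28 = 756. Cycles 6 to 28 give 23 starts. The even-numbered ones run from 6 to 28, so **12** have no scheduled count.
- Under 6.1.1 the number is 0 in both cases.

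**Interval between scheduled counts after Cycle 5**

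- Section 7: 2 × 28 = 56 days nominal. Section 6.1.1: 28 days.
- With the visit windows, the Section 7 interval can reach 56 + 3 + 7 = 66 days from Cycle 5 to Cycle 7, and 56 + 7 + 7 = 70 days afterwards.

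**Sensitivity to dose delays**

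Section 1.1 reports dose delays in 45% of patients on palbociclib plus letrozole, so uninterrupted cycles give an upper bound for a given treatment duration. The documents do not give the length of the delays, so the mean cycle length below is an assumption. The last cycle started is the whole number of cycle lengths in the period, plus 1.

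| Assumed mean cycle | Even starts from Cycle 6, 15 months | Even starts from Cycle 6, 25 months |
|---|---|---|
| 28 days | 6 | 12 |
| 30 days | 6 | 11 |
| 32 days | 5 | 10 |
| 35 days | 5 | 9 |

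**The case against.** The strongest reply is that the two schedules can both be met. Section 7 does not forbid extra counts, 6.1.1 is binding, and anyone applying Table 2 has the 6.1.1 sentence in front of them. That is true, but a site meets both only by adding counts that the calendar omits, while Section 6 itself refers laboratory timing to Section 7.

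A second reply is that two-cycle monitoring was intended. The calendar, footnote 16, 7.2.5 and 7.3 agree with one another, which looks deliberate. Footnote 4 also speaks of every cycle for the pregnancy test (where clinically indicated) although its row likewise moves to two-cycle visits, so the phrase may be loose wording. This may be right. It would make 6.1.1 the sentence to amend; it would not remove the contradiction.

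Third, the clinical exposure may be small. Section 10.1 gives a median of 15 days to first neutropenia, so most first episodes should fall in Cycles 1 to 5, where both sections require counts. It also gives a median of 7 days for Grade 3 or worse episodes, and palbociclib is not taken on Days 22 to 28, so many episodes may have resolved by the next Day 1. This limits the claim and is accepted. It does not exclude later recurrence: Table 2 requires no dose reduction after uncomplicated Grade 3 haematological toxicity. The repeat count one week later helps only once a count has shown Grade 3.

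Finally, the figures count opportunities, not harms, and treatment may stop before progression for other reasons. That stands.

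**Conclusion.** The concern holds: current operative text contradicts itself, and no footnote or precedence clause resolves it. Whichever schedule was intended, one passage is wrong as written. A site following Section 7 exactly has no scheduled count at 6 cycle starts over 15 months of treatment and 12 over 25 months, or 5 and 9 if the mean cycle is 35 days. These figures assume treatment for the full period, and the cycle lengths above 28 days are assumed.

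The consequence is confined to safety monitoring and protocol compliance from Cycle 6. Whether Grade 3 toxicity can be detected, and the hold applied, at those starts depends on which section the site reads. The documents give no rate of Grade 3 or worse counts at later cycle starts, so the number of missed holds cannot be estimated. No material effect is claimed on PFS, the sample size or the per-subject adverse-event proportions. The inconsistency should be fixed, because it concerns a patient-safety rule and the repair is small.

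**What to change.** Choose one schedule and state it in both places.

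1. **If a count at every cycle is intended:** add Day 1 platelets, ANC and haemoglobin at each cycle from Cycle 6 to the calendar row, footnote 16 and Section 7.3. State that the second dispensed cycle may not start until that count has been reviewed under Table 2. The cost is one routine blood draw per even-numbered cycle, about 6 over 15 months or 12 over 25 months of uninterrupted treatment, which 6.1.1 already requires. No extra dispensing visit is needed.
2. **If two-cycle monitoring after Cycle 5 is intended:** amend the 6.1.1 sentence accordingly, and state in Table 2 which result governs the start of the second dispensed cycle. This adds no draws.

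The first option is the safer default because it makes the Table 2 hold workable at every cycle start. Either is a short protocol clarification, and either settles whether a missing even-cycle count is a deviation.

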### **6.1.2.** Tamoxifen Dose Modifications

The established clinical dose of tamoxifen (20 mg/day) will be used and no dose modification of tamoxifen is planned in this study.

For information on tamoxifen and management of tamoxifen related adverse events refer to the Tamoxifen SmPC or Prescribing Information.

# 6.1.3. Goserelin (or equivalent) Dose Modifications

The established clinical dose of goserelin (3.6 mg subcutaneous injection every 28 days or 10.8 mg subcutaneous injection every 12 weeks) may be used and no dose modification of goserelin is planned in this study.

For information on goserelin and management of goserelin related adverse events refer to the Zoladex® SmPC or Prescribing Information.

The established clinical dose of leuprolide (3.75 mg intramuscular injection every 28 days or 11.25 mg intramuscular injection every 12 weeks) may be used and no dose modification of leuprolide is planned in this study.

For information on leuprolide and management of leuprolide related adverse events refer to the Lupron® SmPC or Prescribing Information.

# 7. STUDY CALENDAR & EVALUATIONS

[Cycle = 28 days]							T		
	Scree	ening	Cycle 1	Cycle 2	Cycle 3-5	Every 2 cycles	Every 3 cycles	Safety follow up	Long-Term follow up
Study Day	-28 days	-14 days	Day 1 	Day 1 (±3)	Day 1 (±3)	(± 7)	(± 7)	30 days (±7) post last study drug	Every 3 months (±14) for 2 years from registration
REQUIRED ASSESSMENTS									
Informed Consent/ HIPAA auth.	X								
Medical hx including prior therapies; pathology	X								
Physical examination	X		X	X	X	C7+		X	
Vital Signs, weight, height (screen only)	X		X	X	X	C7+		X	
ECOG status	X		X	X	X	C7+		X	
Baseline signs/ symptoms; AE assessment	X		X	X	X	C7+		$X^5$	
Concomitant medications	X		X	X	X	C7+		X	
Survival									$X^6$
LABORATORY TESTS									
Blood Chemistries 		X	X	X	X	C7+			
Platelets, ANC & Hgb 		X	D1, D15	D1, D15	X	C7+			
Pregnancy test for WOCP 		-72h	X	X	X	C7+			
DISEASE ASSESSMENT 						C3-19	C22+		
CT/MRI chest, abdomen/pelvis	X					$X^8$	$X^8$		X
CT or MRI Brain, if clinically indicated	X								
Whole body bone scan	X					$X^{8,9}$	$X^{8,9}$		
Bone x-ray, CT, or MRI 	X					$X^8$	$X^8$		
Skin color photography, if applicable	X					$X^8$	$X^8$		
TREATMENT EXPOSURE									
Palbociclib (Day 1-21)			X	X	$X^{16}$	$C7+^{16}$			
Tamoxifen (Continuous)			х —		—	C7+			
CORRELATIVE STUDIES (SPECIMEN COI	LLECTI	ION)					C8, 11, etc.		
Tumor tissue (unstained slides) 			X					$X^{11}$	
Blood for circulating tumor DNA 			X		C5		$X^{12}$	$X^{12}$	
BANKING SAMPLES (SPECIMEN COLLECTION)									
Whole Blood 			X						
Unstained Slides  (archival, if available)			X						
Serum and Plasma 			X					X	

#### Footnotes:

- 1: For cycle 1 only: labs do not need to be repeated if done within 7 days of day 1.
- 2: Blood Chemistries to include: sodium, potassium, serum creatinine (or GFR; see 3.1.8), calcium, albumin, ALT, AST, bilirubin, alkaline phosphatase.
- 3: For Cycles 1 and 2 only, hematology assessments done on Day 1 and also on Day 15
- 4: A negative serum or urine pregnancy test is required within 72 hours of study registration and at the beginning of each cycle, if clinically indicated. If the urine test cannot be confirmed as negative, a serum pregnancy test will be required.
- 5: For subjects with unresolved treatment-related toxicity, follow as medically appropriate until resolution or stabilization
- 6: Survival assessment to be recorded every 3 months until 2 years from registration
- 7: Appropriate scans to assess disease status will be obtained within 28 days of study enrollment including CT chest, abdomen/pelvis. PET/CT: The CT portion of PET/CT is usually of lower quality and should typically not be used in place of dedicated diagnostic CT. However, if the CT portion is of diagnostic quality, it may be used.
- 8: Disease assessment will be performed on Day 1 of every 2 cycles starting at cycle 3 (ex. Day 1 of cycle 3, 5, 7, etc.) for the first 19 cycles (18 months). Disease assessment will be performed on Day 1 of every three cycles starting at cycle 22 (ex. Day 1 of cycle 22, 25, etc.) until discontinuation of study drug.
- 9: Bone scan will be repeated as per footnote 8 above only if positive for bone mets at the time of screening or if clinically indicated.
- 10: If bone lesion(s) detected from whole body bone scan, perform bone x-ray, CT or MRI of the largest bone metastatic area.
- 11: Histological confirmation of breast cancer diagnosis is required (Section 3.1.3). Although not required as a protocol procedure, a patient with a new metastatic lesion should be considered for biopsy whenever possible to reassess ER/PR/HER2 status, if clinically indicated. Also, biopsy at the time of progression should be considered as clinically indicated, but it is not required as a protocol procedure. If a biopsy is prospectively done as standard of care, the study would like to collect samples for correlative research. Unstained slides from either the fresh biopsy or from an archival tumor specimen (metastatic lesion) may be submitted at baseline.
- 12: Blood for circulating tumor DNA will be collected cycle 1 day 1, cycle 5 day 1 and day 1 of every subsequent 3rd cycle (e.g. cycle 8, 11, etc.), and at time of progression.
- 13: Submission of whole blood for banking is to be collected at Pre-Treatment Cycle 1 Day 1. See CLM for collection, processing, labeling and shipping instructions.
- 14: Submission of unstained slides for banking from an archived FFPE tumor block (if available). See CLM for collection, labeling, and shipping instructions.
- 15: Submission of serum and plasma for banking are to be collected at Pre-Treatment Cycle 1 Day 1 and at the 30 Day Safety Follow up visit. See CLM for collection, labeling, processing, and shipping instructions.
- 16: After cycle 5, subjects will be assessed every 2 cycles (cycle 7, 9, 11, etc.). Two cycles of palbociclib may be dispensed from cycle 5 onward.

